### **8.5.2. Method of Detecting AEs, TEAEs, SAEs and TESAEs**

The method of recording, evaluating, and assessing causality of AEs, TEAEs, SAEs and TESAEs, and the procedures for completing and transmitting SAE reports are provided in Section 10.2, Appendix 2.

Care will be taken not to introduce bias when detecting AEs and/or SAEs. Open-ended and non-leading verbal questioning of the Participant is the preferred method to inquire about AE occurrences.

### **8.5.3. SAE Reporting to the Sponsor or Designee**

All SAEs should be reported to the Sponsor or designee within 24 hours of knowledge of the SAE occurring.

### **8.5.4. Adverse Events of Special Interest**

#### **Categories of AESIs**

There are three main categories of AESIs as presented below: 1) those considered to be related to the angiogenesis potential of Engensis, 2) other medical problems in this patient population, and 3) injection site reactions.

#### **8.5.4.1. AESI Considered Related to Angiogenesis**

##### Atherosclerosis

Hyperplasia of the vasa vasorum in the early stages of atherosclerosis is independent of angiogenesis, but the intimal neovascularization that follows the hyperplasia of the vasa vasorum is angiogenesis-dependent. Angiogenesis increases oxygen and nutrients to the artery wall and supports initial plaque growth. Once the atherosclerotic plaque develops, intimal angiogenesis is thought to contribute to characteristics of an unstable plaque, plaque hemorrhage, and plaque rupture. Therefore, diagnoses suggestive of recent coronary artery disease since Baseline will be evaluated as AESIs.

##### Cancer

Angiogenesis plays an important role in the proliferation and metastatic spread of cancer as these processes are dependent on an adequate supply of oxygen and nutrients and removal of waste products. All types of cancer reported after randomization will be deemed to be AESIs.

#### **8.5.4.2. Other Medical Problems in ALS Patients**

Several medical problems are frequently observed in patients with ALS that should be considered AESIs. These medical problems are listed below.

- Pulmonary Medical Problems: Because patients with ALS are at an increased risk to develop pulmonary medial problems such as aspiration of food or liquids, pneumonia,

---

and respiratory arrest, all events of this type that occur after randomization will be considered AESIs.

- **Progressive Muscle Weakness:** Because some patients with ALS may develop rapidly progressive muscle weakness that results in loss of ability to care for self, decubitus ulcers, or weight loss due to impaired deglutition, all events of this type that occur after randomization will be considered AESIs.
- **Bulbar Disease:** Participants may develop bulbar disease or worsening on bulbar disease following randomization manifested as challenges with dysarthria, facial weakness, impaired tongue pulsion or palate elevation, and impaired mastication and swallowing; all of these types of events that occur after randomization will be considered AESIs.

#### **8.5.4.3. Injection Site Reactions**

The most common ISRs in the prior Phase 1/2 study in ALS Participants were local pain and bruising at the site of injection. A follow-up notification for ISRs will occur within 2 to 3 days after each Study Injection Visit. The location and temporal relationship to the most recent injections will determine whether the event is an ISR and should be reported as a TEAE. For an AE to qualify as an ISR, the reaction must be located in close proximity to an injection site and be first observed and graded within 48 hours following Study Injections. ISRs that remain unresolved after 48 hours will continue to be assessed at subsequent Visits as ongoing AEs until resolved.

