**16. Revised Amyotrophic Lateral Sclerosis Functional Rating Scale (ALSFRS-R)** will be performed at the Clinical Site at Screening, predose on the Days 0, 60, and 120, and on Days 30, 84, 144, and 180/ET.

**17. Handheld Dynamometry (HHD)** will be measured at the Clinical Site predose on Days 0, 60, and 120, and at Visits on Days 30, 84, 144, and 180/ET.

**18. ATLIS** will be measured (only at sites that have the ATLIS equipment) predose on Days 0, 60, and 120, and at Visits on Days 30, 84, 144, and 180/ET.

**19. Amyotrophic Lateral Sclerosis Assessment Questionnaire, 40 questions (ALSAQ-40)** will be measured predose on Day 0 and at Visits on Days 84 and 180/ET.

**20. Patient Global Impression of Change (PGIC) and Clinical Global Impression of Change (CGIC)** will be conducted at Visits on Days 84 and 180/ET.

**21. Muscle Biopsy:** Biopsies of the gastrocnemius muscle around the injection sites will be collected and stored at Day 0 predose, and Days 84 (optional) and 144 (approximately10 days after the second day of injections of Treatment Cycles 2 and 3).

---

22. **Adverse Events (AEs), Treatment-Emergent Adverse Events (TEAEs), Serious Adverse Events (SAEs) and Treatment-Emergent Serious Adverse Events (TESAEs):** AEs will be recorded after informed consent until the first injections on Day 0. After the start of the 1st Injections on Day 0 through Day 180, AEs will be recorded as treatment-emergent adverse events (TEAEs). Treatment-emergent serious adverse events (TESAEs) occurring after randomization and throughout the study will be recorded. SAEs occurring after the completion of the consent process and before the 1st Injections on Day 0 should be recorded and reported as SAEs only if associated with a protocol-specified procedure. All SAEs, and TESAEs occurring after the time of the 1st Injections through the last Study Visit on Day 180, should be recorded and reported to the Sponsor/designee within 24 hours of awareness of the SAE/TESAE by the Site.

23. **Adverse Events of Special Interest (AESIs):** All AESIs will be continuously monitored throughout the study.

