24. **AESI: Injection Site Reactions (ISRs)** must be initially assessed immediately after all injections at an Injection Visit. The Investigator or designee will follow up with the Participant within 2 to 3 days after Study Injections to ask the Participant about reactions at any injection sites and, if any are noted, the worst reaction will be recorded as a TEAE and considered an AESI.

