#### 10.4.2. Definitions

Active Infection	Chronic infection or severe active infection that may compromise the Participant's wellbeing or participation in the study, in the Investigator's judgment
Day 14, etc.	Day 14 (for example) refers specifically to the actual day of the Visit designated as the Day 14 Visit, and not to the 14 th day of the study for a Participant.
End of Study	Completion of the last Visit or procedure shown in the Schedule of Activities for the last Participant remaining in the study

Highly Effective Contraception Method	See Contraceptive Guidance
Injection Site Reaction	An AE located in close proximity to the injection sites on the target muscles and first observed within 48 hr following Study Injections
Investigator	The PI or appropriate study site personnel whom the PI designates to perform a certain duty
Placebo	Placebo comprises 45 mg sodium chloride and 55 mg sucrose in 5 mL water for injection. Engensis vials contain the same excipients.
Safety Analysis Population	All Participants who receive at least one Study Injection
Sponsor	Helixmith Co., Ltd. and its representatives contracted to provide services for study conduct
Study Drug	Engensis or Placebo
Study Injection	Injection of Engensis or Placebo
Participant	Anyone who is consented for Screening
Treatment Arm	The group of Participants assigned to receive Study Drug or the group assigned to receive Placebo during the first 6 months of treatment
Treatment Cycle	Two sets of Study Injections 14 days apart comprising a single dose
VM202	The active pharmaceutical ingredient of Engensis: a novel genomic complementary deoxyribonucleic acid (cDNA) hybrid human hepatocyte growth factor (HGF) coding sequence (HGF-X7) expressing two isoforms of HGF, HGF 728 and HGF 723

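### ISR status under Protocol 8.5.4.3 depends on observation and grading by 48 hours, but the only scheduled ISR contact after the injection visit may come as late as 72 hours

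*Protocol*

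**What the plan says.** Protocol 8.5.4.3 sets two conditions for an ISR. The reaction must lie close to an injection site, and it must "be first observed and graded within 48 hours following Study Injections". The same section schedules the later check: "A follow-up notification for ISRs will occur within 2 to 3 days after each Study Injection Visit". It also states a general principle: "The location and temporal relationship to the most recent injections will determine whether the event is an ISR".

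The glossary in Protocol 10.4.2 defines an ISR as "An AE located in close proximity to the injection sites on the target muscles and first observed within 48 hr following Study Injections". It does not mention grading.

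Footnote 24 of the Schedule of Activities says how ISRs are collected. They "must be initially assessed immediately after all injections at an Injection Visit". Then, "The Investigator or designee will follow up with the Participant within 2 to 3 days after Study Injections to ask the Participant about reactions", and "if any are noted, the worst reaction will be recorded as a TEAE and considered an AESI". No hour limit is attached. Footnote 23 adds: "All AESIs will be continuously monitored throughout the study". Appendix 3 asks for each limb to be graded after each treatment but gives no time for it.

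ISR incidence is a primary endpoint (Protocol 9.3.1, SAP 3.1), and 9.3.1 rules out formal testing of safety. SAP 6.14.1 reports it in Table 14.3.1.8. It also makes ISRs the third of four AESI categories, which feed Table 14.3.1.10. The SAP states no ISR time window and does not say which protocol definition selects the events.

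**The concern.** The 48-hour window presumably exists to tie a reaction to the injections that caused it, which is a matter of when the reaction began. Section 8.5.4.3 instead sets the clock on when the reaction was seen and graded. A reaction absent at the immediate check has no guaranteed ISR check until a contact that may fall on either side of the limit. Two participants with the same bruise, starting at the same hour, could then be classified differently because one was contacted sooner.

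At stake is the case definition of a primary endpoint. Because the analysis is descriptive, the reported percentage is the result, and its meaning rests on that definition. The same choice may decide whether an event enters the AESI table.

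**Working it through.** The plan gives no figure to reproduce, so the check compares times and wording.

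**1. Contact window in hours.** The inputs are the 48-hour limit (8.5.4.3, 10.4.2) and the contact within 2 to 3 days (8.5.4.3, footnote 24). The window can be read in three ways.

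- Upper limit: any time up to 3 × 24 = 72 h. Then 48/72 = 67% of the permitted interval lies inside the limit and hours 48 to 72 lie outside it. This is a share of permitted time, not of contacts.
- Elapsed time: 2 × 24 = 48 h to 3 × 24 = 72 h, so at or after the limit.
- Calendar days, assuming that injections end and contacts occur between 09:00 and 17:00: day 2 is 48 ± 8 = 40 to 56 h, and day 3 is 72 ± 8 = 64 to 80 h. All day-3 contacts miss the limit.

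On the calendar reading, take contact times as uniform over 09:00–17:00 (assumption) and let T be the clock time at which injections end. The share of day-2 contacts after 48 h is the mean of (17 − T)/8:

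- T uniform 09:00–17:00: 4/8 = 50%
- T uniform 10:00–17:00: 3.5/8 = 44%
- T uniform 12:00–17:00: 2.5/8 = 31%

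These are shares of contacts, not of reactions.

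**2. Does any other scheduled check fill the gap?** The nominal gaps from the six injection visits to the next clinic visit are 14, 16, 14, 10, 14 and 10 days. The visit windows shorten the gap most for Day 74 to Day 84: (84 − 3) − (60 + 3 + 15) = 3 days. Day 134 to Day 144 gives the same: (144 − 3) − (120 + 3 + 15) = 3 days. So no clinic visit falls inside 48 hours. Vital signs 2 hours after dosing do, but they are not described as an ISR check. A spontaneous report is possible under footnote 23 but is not scheduled.

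**3. The passages side by side.**

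| Event | 8.5.4.3 | 10.4.2 | Footnote 24 |
|---|---|---|---|
| Present and graded at the immediate check | ISR | ISR | Within the ISR assessment |
| Participant notices it at hour 10; reported and graded at hour 60 | Not an ISR | ISR if the participant's own observation counts | Recorded as TEAE and AESI if it is the worst reaction |
| Onset at hour 55; reported at hour 60 | Not an ISR | Not an ISR | Recorded as TEAE and AESI if it is the worst reaction |

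The second row is the problem: onset is inside the window, yet 8.5.4.3 excludes the event. In the third row the two definitions agree, and the only open point is that footnote 24 is silent on time.

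**4. Size.** The rule applies at 6 × 18 = 108 planned injection visits (72 Engensis, 36 Placebo). A participant's overall ISR status changes only if all of that participant's ISRs over the six visits are reclassified. In a preferred-term row it changes only if all of the participant's ISRs under that term are. One such participant moves incidence by 1/12 = 8.3 points or 1/6 = 16.7 points. These are the sizes of one unit, not estimates of the effect.

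**The case against.** The strongest reply has four parts.

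- The contact is *within* 2 to 3 days, which permits a call before hour 48. This is right. A reader might infer that the contact always misses the limit, but the text does not support that. What stands is that the plan also permits a contact between hours 48 and 72, and a reaction first graded then fails 8.5.4.3.
- Footnote 24 is a collection instruction that says AESI, not ISR, so it is not a rival definition. This also stands. A reader might count three competing definitions. There are two, differing by the grading condition, plus a recording instruction under an ISR heading with no time limit.
- 8.5.4.3 already says that location and timing relative to the injections decide ISR status, and the contact exists to ask participants what they noticed. That supports an onset reading, but the next condition in the same section requires observation and grading by 48 hours. Participant observation may satisfy the first part; it does not satisfy the second.
- Much of the remedy already exists. SAP 6.2.5 has a rule for missing event start times, which implies that start times are collected. Table 14.3.1.2 and Listing 16.2.7.1 carry late-graded events without a 48-hour filter. This is fair, and it makes an extra supportive table optional. It does not settle which events enter Table 14.3.1.8.

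**Conclusion.** The concern holds in limited form. Applied as written, 8.5.4.3 removes from the primary ISR table some reactions that began within 48 hours, solely because they were reported or graded later. Protocol 10.4.2 could admit the same events, and the SAP does not choose between them. Entry into AESI Table 14.3.1.10 may be affected too.

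A reader might infer a bias between arms or a loss of safety data. The documents support neither. Participants, Investigators and Site staff other than the unblinded pharmacy staff are blinded (Protocol 6.3.2), so no direction is known, and excluded events remain TEAEs. Reactions present and graded at the immediate check are unaffected.

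The number of reactions affected cannot be derived from the documents. The shares of contacts above rest on assumed clock times. The wording mismatch itself needs no assumption. It is worth correcting because the endpoint is primary, each participant weighs heavily at 12 and 6 per arm, and the correction is cheap.

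**What to change.** Reconcile Protocol 8.5.4.3, Protocol 10.4.2 and Schedule of Activities footnote 24 to one definition: reported onset within the protocol's stated window after the most recent injections, regardless of when the reaction is reported or graded. Footnote 24 can remain a collection instruction with a cross-reference to that definition.

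In the SAP, state that this rule selects events for Table 14.3.1.8 and the ISR category of Table 14.3.1.10, using the recorded start date and time. Confirm on the eCRF that both are collected for ISRs. Also say how incomplete start dates are handled. SAP 6.2.5 moves a wholly missing start date to the first dose when the event is ongoing or stopped on or after that date, which could place a later reaction inside the first window.

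A separate table of all injection-site events regardless of onset is optional.

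The cost is wording in three protocol places, a short SAP addition, and onset fields on the form if they are absent. No visit or contact is added. The downside is some reliance on participants' recall of onset, and possibly a higher ISR count.

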#### **8.5.5. Follow-up of AEs, TEAEs, SAEs, and AESIs**

After the initial AE/TEAE/SAE report, the Investigator is required to proactively follow each Participant at subsequent Visits/contacts. All SAEs and AESIs (see Section 8.5.4) will be followed until resolution, stabilization, the event is otherwise explained, or the Participant is lost to follow-up (as defined in Section 10.2.4, Appendix 2).

#### **8.5.6. Regulatory Reporting Requirements for SAEs**

Prompt notification by the Investigator to the Sponsor of an SAE is essential to ensure that legal obligations and ethical responsibilities towards the safety of Participants and the safety of a study drug under clinical investigation are met.

The Sponsor has a legal responsibility to notify both the local regulatory authority and other regulatory agencies about the safety of a study drug under clinical investigation. The Sponsor will comply with country-specific regulatory requirements relating to safety reporting to the regulatory authority, Institutional Review Boards (IRBs), and Investigators.

For all studies, Investigator Safety Reports must be prepared for suspected unexpected serious adverse reactions (SUSARs) according to local regulatory requirements and Sponsor policy and forwarded to Investigators as necessary.

---

An Investigator who receives an Investigator Safety Report describing an SAE or other specific safety information (e.g., summary or listing of SAEs) from the Sponsor will review and then notify the IRB if appropriate according to local requirements.

### **8.5.7. Sponsor's Responsibility**

All AEs and SAEs will be reported on an annual basis to FDA in accordance with the IND regulation (21 CFR 312). Per the 2010 FDA Guidance Document for Industry and Investigators “Safety Reporting Requirements for INDs and BA/BE Studies,” events categorized as “possibly” or “probably” related will be treated as “suspected adverse reactions.” Events categorized as “definitely” related will be treated as an “adverse reaction.”

All serious and unexpected study-drug-related or suspected adverse reactions will be reported to FDA and to all participating Investigators in an IND Safety Report within 15 calendar days of the event after the Sponsor determines that the suspected adverse reaction qualifies for reporting (21 CFR 312.32). Any unexpected fatal or life-threatening study-drug-related adverse reaction or suspected adverse reaction will be reported to the Agency within 7 calendar days after the Sponsor’s initial receipt of the information.

The Sponsor will notify all participating Investigators of any new safety information that alters the current risk-benefit assessment of the study medication or that would be sufficient to consider changes in Engensis administration or in the overall conduct of the study.

### **8.5.8. Pregnancy and Contraception**

#### **8.5.8.1. Pregnancy Test (Women of Childbearing Potential Only) and Contraception**

Female Participants must be nonpregnant, nonlactating, and either postmenopausal for at least 1 year, or surgically sterile for at least 3 months, or agree to use double-barrier contraception from 14 days prior to randomization and/or their last confirmed menstrual period prior to study randomization (whichever is longer) until 2 months after the last visit on Day 180.

Double-barrier contraception may include, but is not limited to, intrauterine device with spermicide, female condom with spermicide, diaphragm with spermicide, cervical cap with spermicide; having a male sexual partner who agrees to use a male condom with spermicide; or having a sterile sexual partner.

For women of childbearing potential, a urine beta human chorionic gonadotropin ( $\beta$ -HCG) test will be performed during Screening and before randomization (Day 0); results of the test must be negative. The  $\beta$ -HCG test will also be performed at Day 180/ET to evaluate whether the Participant is pregnant.

The rhythm method is not considered acceptable method of contraception.

#### **8.5.8.2. Pregnancy**

The Investigator will collect pregnancy information on any female Participant who becomes pregnant while participating in this study. The initial information will be submitted to the Sponsor within 24 hours of learning of a Participant’s pregnancy.

---

Further dosing will be discontinued for any female Participant who becomes pregnant during the study.

The Participant will be followed to determine the outcome of the pregnancy. The Investigator will collect follow-up information on the Participant and the neonate, and the information will be forwarded to the Sponsor. Generally, follow-up will not be required for longer than 6 to 8 weeks beyond the estimated delivery date.

While pregnancy itself is not considered to be an AE or SAE, any pregnancy complication or elective termination of a pregnancy for medical reasons will be reported as an AE or SAE. A spontaneous abortion (occurring at < 22 weeks gestational age) or stillbirth (occurring at > 22 weeks gestational age) is always considered to be an SAE and will be reported as such. Other abnormal pregnancy outcomes (e.g., fetal death, congenital anomalies, ectopic pregnancy) are also considered SAEs and will be reported.

Any post-study pregnancy-related SAE considered possibly, probably, or definitely related to the study drug by the Investigator will be reported to the Sponsor. While the Investigator is not obligated to actively seek this information in former study Participants, he or she may learn of an SAE through voluntary reporting.

The Investigator will record a narrative description of the course of each pregnancy and its outcome.

#### **8.5.9. Disease-Related Events and/or Disease-Related Outcomes Not Qualifying as AEs or SAEs**

Except for signs and symptoms of ALS (i.e., numbness, pain, tingling or burning sensation, cramps, and increased sensitivity to touch), all disease-related events or disease-related outcomes qualify as AEs or SAEs.

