## 2.2. **Background**

### 2.2.1. **Pathophysiology of Amyotrophic Lateral Sclerosis**

Amyotrophic Lateral Sclerosis (ALS) is an adult-onset neurodegenerative disorder characterized by the loss of upper and lower motor neurons. The disease is diverse in its presentation, cause, and progression, but, in general, ALS presents clinically as asymmetric muscle weakness, wasting, spasticity, weight loss, dysphagia, and paralysis; in 10% to 15% of patients, cognitive impairment may arise before or following that of motor neuron dysfunction. Pathologically, ALS is characterized by progressive degeneration and loss of motor neurons in the spinal cord, brainstem, and cerebral cortex. From the time of diagnosis, median survival is 3 to 5 years; about 10% of patients can survive for  $\geq 10$  years. While the majority of ALS cases are sporadic (primary or idiopathic), about 5% to 10% of patients have a positive family history (familial ALS), with a mutation in the Cu/Zn superoxide dismutase 1 (SOD1) gene accounting for 10% of familial ALS.

Estimates of the incidence of ALS worldwide range from 1 to 3 cases per 100,000 people annually, with a higher incidence in Caucasians, in people who smoke, and in several geographic regions in which environmental toxins are suspected. The ALS Association, the Centers for Disease Control and Prevention, and the National Institute of Neurological Disorders and Stroke estimate that as many as 30,000 Americans may have the disease at any given time, with approximately 5,600 newly diagnosed patients annually.a

a <http://www.alsa.org/about-als/who-gets-als.html> (accessed October 12, 2015);  
<http://www.cdc.gov/als/WhatisALS.aspx> (accessed October 12, 2015);  
[http://www.ninds.nih.gov/disorders/amyotrophicsclerosis/detail\\_ALS.htm](http://www.ninds.nih.gov/disorders/amyotrophicsclerosis/detail_ALS.htm) (accessed October 12, 2015)

undergo transcriptional dysregulation and abnormal ribonucleic acid (RNA) processing which,

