#### **2.2.4. Engensis and VM202**

The investigational agent (study drug) being studied in this protocol is Engensis, which contains the active pharmaceutical ingredient VM202. VM202 is a plasmid DNA that contains the novel genomic complementary DNA (cDNA) hybrid human HGF coding sequence (HGF-X7) expressing two isoforms of HGF, HGF728 and HGF723 (Figure 2).

[REDACTED]

[REDACTED]

[REDACTED] [REDACTED]

[REDACTED] [REDACTED] [REDACTED]

[REDACTED] has been evaluated for general toxicity following single IM and

[REDACTED]

[REDACTED]

[REDACTED] [REDACTED]

[REDACTED]

[REDACTED]

[REDACTED]

[REDACTED]

---

artery disease (Phase 2), one study in coronary artery disease (Phase 1), four studies (Phase 1/2, Phase 2, and two Phase 3) in Participants with painful DPN, a study (Phase 1/2) in ALS, and one (Phase 3) study in diabetic Participants with chronic nonhealing foot ulcers (NHU). Engensis was well tolerated, the most frequent reaction being pain at injection sites in 1-4% of Participants, which was similar to that observed in the placebo groups. No systemic effects have been attributed to Engensis.

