### Adverse Events in Clinical Studies

Engensis has been well tolerated in all clinical studies conducted thus far in more than 500 Participants. The preponderant adverse events have consisted of mild, transient injection site effects, including itching, erythema, pain, and muscle spasms. Other treatment-emergent adverse events (TEAEs) that have been reported were generally mild to moderate. Refer to the IB for a table of AEs that occurred in  $\geq 2\%$  of trial Participants.

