### 5.1. Inclusion Criteria

1. Male or female Participants age  $\geq$  18 years, but  $\leq$  80 years, at time of completion of the informed consent process
2. Clinically definite or probable Amyotrophic Lateral Sclerosis (ALS) or laboratory-supported probable ALS as defined in the revised El Escorial/Airlie House diagnostic criteria
3. The site of onset of ALS symptoms is a limb and experiencing symptoms of lower motor dysfunction (e.g., weakness, atrophy, cramps, poor circulation, etc.) with upper motor neuron symptoms (e.g., brisk reflexes, spasticity)
4. Onset of ALS symptoms  $\leq$  4 years
5. Slow Vital Capacity (SVC)  $\geq$  50% of predicted value at Screening
6. Not taking riluzole, or on a stable dose (defined as no noted toxicities) for at least 30 days prior to Screening and throughout the study
7. Not taking edaravone or on a maintenance cycle for at least 30 days prior to Screening and throughout the study
8. For females of childbearing potential, a negative urine pregnancy test at Screening and on Day 0
9. Male Participants and their female partners must agree to use double-barrier contraception during the study or provide proof of postmenopausal state (minimum 1 year) or surgical sterility
10. Male Participants must not donate sperm during the study
11. Female Participants must be nonpregnant, nonlactating, and either postmenopausal for at least 1 year, or surgically sterile for at least 3 months, or agree to use double-barrier contraception from 28 days prior to randomization (Day 0) and/or their last confirmed menstrual period prior to study randomization (whichever is longer) until the end of the study
12. Capable of complying and willing to comply with the requirements and restrictions in the informed consent form and this protocol
13. Willing to forgo new experimental ALS treatments for at least 6 months following randomization

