#### 10.2.2. Definition of TEAE

Treatment-Emergent Adverse Event is defined as:

- An event that emerges during treatment, having been absent at pretreatment, or worsens relative to the pretreatment state, as defined in the E9 Guidance.
- The TEAE is not related to causality / drug relatedness. It may or may not be related to the drug but is considered a TEAE due to its appearance at or after the treatment has been administered.

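### Protocol 8.5.9 lets new or worsened pain, cramps and sensory symptoms attributed to ALS go unrecorded, in conflict with the AE and TEAE definitions in Appendix 2

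*Protocol*

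**What the plan says.** Protocol 8.5.9 carves one group out of AE and SAE status: "Except for signs and symptoms of ALS (i.e., numbness, pain, tingling or burning sensation, cramps, and increased sensitivity to touch), all disease-related events" or outcomes qualify. The list is introduced by i.e., so it reads as a definition rather than as examples. It does not mention onset, change from baseline, severity or location.

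Four other parts of the plan bear on the same events:

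- **Protocol 10.2.1 (Appendix 2)** counts as AEs any condition first found after dosing and any flare of a pre-existing one. It excludes symptoms of the disease under study only when they are no worse than that participant's ALS would lead one to expect.
- **Protocol 10.2.2** defines a TEAE as "An event that emerges during treatment, having been absent at pretreatment, or worsens relative to the pretreatment state" and says that cause plays no part.
- **Protocol 8.5.4.3** counts a reaction as an injection site reaction (ISR) only if it is close to an injection site and must "be first observed and graded within 48 hours following Study Injections". Note 24 to the Schedule of Activities has sites ask about reactions two to three days after each injection visit and record the worst as a TEAE.
- **SAP 6.14.1** gives a broad AE definition without the 8.5.9 exception. It tabulates TEAEs by system organ class and preferred term.

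TEAE and TESAE incidence is a primary endpoint (Protocol 9.3.1).

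**The concern.** The exception names symptoms that a participant might well report after 128 intramuscular injections in a day, and labels them as disease. Pain is the clearest case. The protocol's summary of clinical experience describes "the most frequent reaction being pain at injection sites in 1-4% of Participants", and its risk section lists "mild, transient injection site effects, including itching, erythema, pain, and muscle spasms" as the main adverse effects.

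If a site follows 8.5.9 literally, new limb pain or tingling that is put down to ALS never reaches the AE form. It cannot then be an SAE either, because 10.2.3 says that an event which is not an AE cannot be serious. The SAP's wider definition does not help, since the analysis can count only what was entered. In a trial whose primary objective is safety against Placebo, real treatment effects on these symptoms could be missed.

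**Working it through.** The plan states no figure on this point, so the check compares the text and then gives a scale.

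**1. Does the list match the protocol's own ALS?** It holds six symptoms: numbness, pain, tingling, burning, cramps, touch sensitivity.

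- Protocol 2.2.1 describes ALS as "asymmetric muscle weakness, wasting, spasticity, weight loss, dysphagia, and paralysis". Matches: 0 of 6.
- Inclusion criterion 3 gives lower motor symptoms as "e.g., weakness, atrophy, cramps, poor circulation, etc". Matches: cramps only.
- Together 1 of 6 is supported, and 6 − 1 = 5 are not.

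**2. Does the list match known injection effects?** Pain matches exactly. Cramps are close to muscle spasms, and touch sensitivity is close to the tenderness graded in Table 6. Numbness, tingling and burning are not named as injection effects.

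**3. Where does each event go?**

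| Listed symptom, new or worse after dosing | Route | Recorded as TEAE? |
|---|---|---|
| Near an injection site, first seen within 48 h | ISR (8.5.4.3, SoA note 24, Table 6) | Yes |
| Later or elsewhere, not attributed to ALS | 10.2.1, 10.2.2 | Yes |
| Later or elsewhere, attributed to ALS | 8.5.9 says not an AE; 10.2.2 says TEAE | Unclear; can be lost |

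Only the third row is exposed. It is not a narrow time window: Protocol 4.4 puts HGF expression at about 2 to 3 weeks after injection (14 to 21 days), against an ISR window of 2 days. A reaction first reported at a day-3 contact is recordable under SoA note 24 but falls outside the 48-hour definition.

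**4. Weight of one participant.** With 12 and 6 participants (Protocol 5.3), 1/12 = 8.3 points on Engensis and 1/6 = 16.7 points on Placebo, within the incidence of that symptom category.

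**5. Chance of seeing the signal at all.** Let p be the true rate of such symptoms on Engensis and f the share left unrecorded. The documents give neither for late or non-local symptoms, so both are assumed. The chance of at least one recorded case among 12 is 1 − (1 − p(1 − f))^12.

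| p | f = 0 | f = 0.5 |
|---|---|---|
| 1% | 11.4% | 5.8% |
| 4% | 38.7% | 21.5% |
| 10% | 1 − 0.90^12 = 71.8% | 1 − 0.95^12 = 46.0% |
| 20% | 93.1% | 71.8% |

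At p = 10%, f = 0.25 gives 60.8% and f = 0.75 gives 26.2%.

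**6. Effect on the difference.** Equal loss in both arms multiplies the risk difference by (1 − f). An assumed 40% vs 10% (30 points) becomes 20% vs 5% (15 points) at f = 0.5.

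**7. Effect on any-TEAE incidence.** In VMALS-001, 17 of 18 participants (94.4%) had an AE. If that recurs, about 18 × 1/18 = 1 participant in the whole trial would have none. Most participants with an unrecorded symptom would still count through another event.

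**The case against.** The strongest defence is that 8.5.9 concerns disease-related events only. Pain caused by an injection is not disease-related, so it lies outside the sentence; an event is lost only when an investigator attributes it to ALS. Protocol 8.5 sends the reader to Appendix 2 for definitions, and 10.2.1 brings back new conditions and symptoms worse than expected. Local reactions are sought actively and have their own primary endpoint. The ALS descriptions in 2.2.1 and criterion 3 do not claim to be complete. The analysis is descriptive, and the rule applies to both blinded arms.

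Much of this stands, and it rules out several stronger readings that a reader might infer:

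- *All pain and cramps vanish from the primary endpoints.* They do not, given the ISR route and the need for attribution to ALS.
- *A third of the known safety profile is lost, because 26 of 79 AEs in VMALS-001 (33%) were ISRs.* Those were recorded ISRs, the kind of event this plan still captures.
- *The list consists mainly of known injection effects.* Only pain matches exactly.
- *The rule creates a false difference in favour of Engensis.* Applied alike under the blind, it is expected to dilute a difference.

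The defence does not remove the conflict. 8.5.9 itself declares these symptoms to be ALS, which invites the attribution, and it asks for that judgement before recording, whereas 10.2.2 sets cause aside. The causality review in 10.2.5 applies to AEs and SAEs, so an event already ruled out need not reach it. The severity clause in 10.2.1 is missing from 8.5.9, and a new mild or moderate symptom could be excluded even under that clause.

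**Conclusion.** Wrong as written, and it should be fixed; it does not rank as a must-fix. The documents give sites two incompatible rules for listed symptoms that start after 48 hours or away from an injection site and are put down to ALS. Following 8.5.9 can drop events that meet the TEAE definition, and the SAP cannot recover them.

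The likely effect is under-counting at symptom or preferred-term level in both arms, with any difference pulled toward zero. Each lost participant is worth 8.3 or 16.7 points for that symptom category. Any-TEAE incidence is likely to move little, provided that AEs are about as common as in VMALS-001. The detection and dilution figures rest on assumed values of p and f, and the plan gives no basis for choosing among them. Complete loss (f = 1) is a limiting case, not an expectation.

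**What to change.** Replace the exception in Protocol 8.5.9 with a recording rule, for example: any numbness, pain, tingling, burning, cramp or heightened sensitivity to touch that is new, or worse than before the first Study Injection, is recorded as a TEAE whatever its presumed cause. Record which of these symptoms are present at Day 0 before dosing, so that worsening can be judged.

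Deleting only the bracketed list is not enough. It would leave an exemption for all signs of ALS, including the weakness and bulbar events that 8.5.4.2 makes events of special interest.

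Reconcile 8.5.4.3, 8.5.9, 10.2.1 and 10.2.2 with the new rule. That includes the exclusion of expected disease symptoms in 10.2.1, which would otherwise still contradict it. Add a flag for a possible ALS symptom to the AE form, and have SAP 6.14.1 report TEAEs with and without flagged events.

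The cost is a short amendment, a site note, one form field and a repeat of the main TEAE tables. The downside is more mild AE records in both arms and a somewhat higher TEAE incidence; the flag lets a reader see how much of that may be disease.
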